5.3.3.3. Date of Death

Missing or partial death dates will be imputed based on the last contact date:

- If the date is missing it will be imputed as the day after the date of last contact.
- If the day or both day and month is missing, death will be imputed to the maximum of the full (non-imputed) day after the date of last contact and the following:
 - Missing day: 1st day of the month and year of death;
 - Missing day and month: January 1st of the year of death.

5.3.3.4. Date of Start of New Anti-cancer Therapy

Incomplete dates for start date of new anti-cancer therapy (drug therapy, radiation) will be imputed as follows and will be used for determining censoring dates for efficacy analyses and in the derivation of the end of on-treatment period. PD date below refers to PD date by investigator assessment.

- The end date of new anti-cancer therapy will be included in the imputations for start date of new anti-cancer therapy. If the end date of new anti-cancer therapy is:
 - Completely missing then it will be ignored in the imputations below.
 - Partially missing with only year (YYYY) available then the imputations below will consider 31DECYYYY as the end date of the new anti-cancer therapy.
 - partially missing with only month and year available then the imputations below will consider the last day of the month for MMMYYYY as the end date of the new anti-cancer therapy.
- For participants who have not discontinued study treatment at the analysis cutoff date, last dose of study treatment is set to the analysis cutoff date in the imputations below.
- If the start date of new anti-cancer therapy is completely or partially missing then the imputed start date of new anti-cancer therapy is derived as follows:
 - Start date of new anti-cancer therapy is completely missing
Imputed start date = min [max(PD date + 1, last dose of study treatment + 1), end date of new anti-cancer therapy]
 - Only year (YYYY) for start of anti-cancer therapy is available
IF YYYY < Year of min [max(PD date + 1, last dose of study treatment + 1), end date of new anti-cancer therapy] THEN imputed start date = 31DECYYYY;

ELSE IF YYYY = Year of min [max(PD date + 1, last dose of study treatment + 1), end date of new anti-cancer therapy];

THEN imputed start date = min [max(PD date + 1, last dose of study treatment + 1), end date of new anti-cancer therapy];

ELSE IF YYYY > Year of min [max(PD date + 1, last dose of study treatment + 1), end date of new anti-cancer therapy];

THEN imputed start date = 01JANYYYY.

- Both Year (YYYY) and Month (MMM) for start of anti-cancer therapy are available

IF

YYYY = Year of min [max(PD date + 1, last dose of study treatment + 1), end date of new anti-cancer therapy], AND

MMM < Month of min [max(PD date + 1 day, last dose of study treatment + 1 day), end date of new anti-cancer therapy].

THEN

imputed start date = DAY (Last day of MMM) MMM YYYY.

ELSE IF

YYYY = Year of min [max(PD date + 1, last dose of study treatment + 1), end date of new anti-cancer therapy], AND

MMM = Month of min [max(PD date + 1 day, last dose of study treatment + 1 day), end date of new anti-cancer therapy].

THEN

imputed start date = min [max(PD date + 1 day, last dose of study treatment + 1 day), end date of new anti-cancer therapy]);

ELSE IF

YYYY = Year of min [max(PD date + 1, last dose of study treatment + 1), end date of new anti-cancer therapy], AND

MMM > Month of min [max(PD date + 1 day, last dose of study treatment + 1 day), end date of new anti-cancer therapy].

THEN

imputed start date = 01 MMM YYYY.

ELSE IF

YYYY < Year of min [max(PD date + 1, last dose of study treatment + 1), end date of new anti-cancer therapy].

THEN

imputed start date = DAY (Last day of MMM) MMM YYYY.

ELSE IF

YYYY > Year of min [max(PD date + 1, last dose of study treatment + 1), end date of new anti-cancer therapy].

THEN

imputed start date = 01 MMM YYYY.

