13. Bone marrow aspirate and disease assessments will be performed at screening, at Day 16-28 of Cycles 1, 2, or until CR/CRi and MRD negativity are achieved. Then after every 1- 2 cycle as clinically indicated, and at EOT visit (unless previously done within 28 days). Bone marrow aspirates will be analyzed at the study site. A CBC with platelets and differential must accompany each bone marrow assessment. Disease assessments will include clinical evaluation of liver and spleen, and other sites of prior or suspected extramedullary disease. Disease assessments will continue until progression. For those who have not progressed at EOT, disease will be assessed every 12 weeks ( $\pm$ 1 week) up to 1 year from enrollment and every 24 weeks ( $\pm$ 2 weeks) between year 1 and 2, and whenever clinically indicated, until progression. All disease assessment results will be captured in the CRF, even if unplanned or not required by protocol.
14. Minimal residual disease (MRD): Bone marrow aspirate will be collected at screening, investigator suspected CR/CRi, achievement of CR/CRi until MRD negativity before EOT. MRD will be assessed using NGS for rearranged IgH, IgK, and IgL receptor gene sequences at a central laboratory.

Immunophenotyping: performed on peripheral blood or bone marrow aspirate with flow cytometry at screening and will be done in patients with suspected CR and/or CRi. IHC is allowed in patients with a dry tap or otherwise inadequate bone marrow aspirate in the absence of circulating blasts. The leukemia phenotype and/or genotype may also be evaluated by other test methods at the discretion of the investigator.

FISH: Bone marrow aspirates may be analyzed by fluorescence in situ hybridization analysis (FISH) for detection of chromosomal aberrations at screening according to standard of care.

Karyotyping: in all patients, at screening and at least once in patients achieving CR or CRi who had abnormal cytogenetics at baseline. It is recommended that 20 or more metaphases be counted for cytogenetics analysis.

Bone Marrow Biopsy: required at least once, to assess cellularity, in patients with CRi by investigator assessment (ANC  $<1 \times 10^9/L$  and/or platelets  $<100 \times 10^9/L$ ) and as clinically indicated per local standard of care. Biopsies may be also required for inadequate aspirate samples

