**Table 1. Schedule of Activities**

Protocol Activity	Screen  -28 days from enrollment	Cycles 1-6			End of Treatment (EOT) (All patients: 4 weeks from the last dose of study drug)
		Day 1	Day 8	Day 15	

15. Radiological assessments (ie, computed tomography scan or MRI) will be done at screening for patients with suspected extramedullary disease, during study as clinically indicated and to confirm CR or CRi in patients with extramedullary disease at screening. Please use the same method of assessment for each evaluation. Computed tomography scan with contrast is the preferred method of assessment.
16. AEs will be followed until the event or its sequelae resolve or stabilize at a level acceptable to the investigator, or longer if requested by the sponsor. The AE reporting period continues until 9 weeks after the last dose of investigational drug. However, VOD/SOS events, irrespective of the grade, causality, will be reported in the CRF for up to 2 years from first dose and will also be reported as SAEs.
17. Assessment(s) and test(s) done according to standard of care at the institution prior to the patient signing the ICD can be used to determine patient eligibility if collected within the timeframe specified in this protocol, e.g. procedures conducted within 28 days (ECG 3-28 days) prior to enrollment. Results will be recorded in the CRF. However before any collected sample (e.g. ECG, BM aspirate for disease assessment) is sent to the central vendor, the patient must be consented for study participation.
18. Assessment of CNS disease (eg, lumbar puncture) is required at screening in any patient with a prior history of CNS disease or if CNS disease is suspected due to clinical signs and/or symptoms. If a complete CNS assessment is not feasible due to comorbidities, the patient cannot be included in the study. If additional assessments are done at the site, as clinically indicated, results must be collected in the CRF. Patients with history of CNS disease who achieve a CR or CRi must have a CNS assessment to confirm complete response.
19. EOT visits should be performed before starting a new anti-leukemic therapy (including before subsequent hematopoietic stem cell transplant (HSCT) conditioning, other form of consolidation/intensification or maintenance therapy). If a new anti-leukemia therapy will be started, the EOT visit should occur as close as possible to 4 weeks after the last dose of study drug.

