3.5. Safety Endpoints

Safety endpoints will be summarized based on the on-treatment period unless otherwise specified.

On-treatment is defined as the time from the first dose of study treatment through minimum (9 weeks after the last administration of the investigational product, start day of new anti-cancer therapy – 1 day). The start date of new anti-cancer therapy after the first dose of study treatment is derived as outlined in [Section 5.2.5](#). Adverse events occurring on the same day as the first dose of study treatment will be considered to have occurred during the on-treatment period. All other assessments which occur on the same day as the first dose of study treatment will be considered baseline assessments (see [Section 3.4](#) for the definition of baseline). If the exact time is collected, the last assessment before the time of first dose of study treatment will be considered as baseline assessments.

Safety data collected outside the on-treatment period as described above will be listed but not summarized.

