6. ANALYSES AND SUMMARIES

6.1. Primary Endpoint(s)

6.1.1. CR/CRi

6.1.1.1. Main Analysis

The primary endpoint is the incidence of a participant with a best overall response of CR or CRi from date of the first dose to the end of treatment per investigator's assessment according to a modified Cheson Criteria.

Estimand strategy: The analysis applies while on treatment strategy ([Section 2.1.1](#)).

Analysis set: Safety analysis set ([Section 4](#)).

Intercurrent events and missing data: All data collected after an intercurrent event of subsequent anti-cancer therapy is excluded.

Analysis methodology: Test the null hypothesis $H_0: CR/CRi \text{ rate} \leq 37\%$ using the observed sample rate, actual sample size based on single binomial proportion test under normal approximation with empirical estimate of variance, ie, Wald test.

Estimate the CR/CRi rate per investigator's assessment and obtain the corresponding two-sided 95% CI using Wald method and Clopper–Pearson method separately for all participants in the safety analysis set from the time of first dose until the end of treatment. In addition, the frequency (number and percentage) of participants with CR, CRi, and CR/CRi will be tabulated.

Participants with death prior to first post-baseline assessment, new anti-cancer therapy started prior to first post-baseline assessment, and all post-baseline disease assessments missing will be considered as non-responders. Data collected after the end of treatment will be excluded from the analysis.

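### The rule for imputing an incomplete start date of new anti-cancer therapy has no floor at the end-of-treatment visit, so it can end the summarised safety period too early

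*SAP*

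**What the plan says.** SAP 5.3.3.4 covers start dates of new anti-cancer therapy that are missing or partial. The imputed dates "will be used for determining censoring dates for efficacy analyses and in the derivation of the end of on-treatment period".

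- **Completely missing:** "Imputed start date = min [max(PD date + 1, last dose of study treatment + 1), end date of new anti-cancer therapy", closing with a bracket.
- **Month and year known, same month as that reference date:** "imputed start date = min [max(PD date + 1 day, last dose of study treatment + 1 day), end date of new anti-cancer therapy", again closing with a bracket.
- **Month and year known, later month:** "imputed start date = 01 MMM YYYY".
- **Year only:** the reference date if the year matches, or 1 January if the recorded year is later.

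SAP 3.5 ends the on-treatment period at the earlier of 9 weeks after the last dose and the day before new therapy. It adds: "Safety data collected outside the on-treatment period as described above will be listed but not summarized".

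SAP 6.1.1.1 says, for the primary analysis: "All data collected after an intercurrent event of subsequent anti-cancer therapy is excluded". It also counts as a non-responder anyone whose new therapy started before the first post-baseline assessment. SAP 5.2.5 restricts efficacy censoring to the start of new induction therapy.

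Protocol Table 1, footnote 19: "EOT visits should be performed before starting a new anti-leukemic therapy". This includes therapy before HSCT conditioning, and the visit should be as close as possible to 4 weeks after the last dose. Footnote 13 schedules marrows "at Day 16-28 of Cycles 1, 2, or until CR/CRi and MRD negativity are achieved", and again at EOT unless one was done within 28 days.

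**The concern.** The protocol's intended order is last dose, response marrow, EOT visit, then new therapy. The imputation rule knows only the last dose, the PD date and the therapy end date. It can therefore date new therapy before visits that the protocol schedules ahead of it and that are already in the database.

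The imputed date closes the on-treatment period. If it is too early, adverse events in the weeks after the last dose move from the summaries to a listing, and so do the EOT laboratory and ECG results. Reported treatment-emergent rates then fall, which flatters the drug. Assessments after the imputed date may also be lost to the efficacy analyses.

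**Working it through.** **Inputs.** Post-dose safety window: 9 weeks = 63 days (SAP 3.5). EOT: day 28 after the last dose (Protocol Table 1; the window is ±3 days). Response marrow: Day 16-28, which is 1 to 13 days after a Day 15 dose. Assumed throughout: no PD after the last dose, and no therapy end date before the imputed date. The true start day T is not in the documents, so it is varied. For orientation, the Phase 3 study had a median of 4.9 weeks (about 34 days) from last dose to HSCT in those who went directly to transplant (Protocol 2.2.2.1.1).

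**Completely missing date.** Imputed start = last dose + 1. The on-treatment period then ends on the last dose date, so 0 post-dose days are summarised. The correct number is min(63, T − 1):

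| True start | Correct post-dose days | Summarised | Lost |
|---|---|---|---|
| day 29 | 28 | 0 | 28 |
| day 35 | 34 | 0 | 34 |
| none within 9 weeks | 63 | 0 | 63 |

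**Month-only date.** If the recorded month is later than the month of last dose + 1, the imputed start is the first of the month. With true start on calendar day c of its month, the imputed start is day T − (c − 1) after the last dose. It falls on or before EOT when T − (c − 1) ≤ 28, that is, when c ≥ T − 27. In a 365-day year with every calendar date equally likely, 12 × (T − 28) dates fail this condition for T up to 56, because every month has at least 28 days:

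| True start T | Share on or before EOT |
|---|---|
| 29 | 1 − 12/365 = 97% |
| 35 | 1 − 84/365 = 77% |
| 42 | 1 − 168/365 = 54% |
| 49 | 1 − 252/365 = 31% |
| 56 | 1 − 336/365 = 8% |
| 63 | 0% |

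Coding the full SAP rule and running it over 730 consecutive last-dose dates gives the same percentages. The same-month branch (exactly last dose + 1) applies in 8% of positions at T = 29 and in none from T = 32. The mean error is about (30.4375 − 1)/2 = 14.7 days early.

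**Dated examples.** Last dose 1 March 2024, true start 30 March recorded as March 2024: imputed 2 March, with EOT due 29 March. Last dose 15 March 2024, true start 16 April recorded as April 2024: imputed 1 April, with EOT due 12 April.

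**Response marrow, month-only date.** The share of positions with the imputed start on or before the marrow depends on the marrow day. Averaged over days 1 to 13 after the last dose it is 28%, 10% and 0.5% for T = 29, 35 and 42. At day 13, the last day of the window, it is 47%, 28% and 5%.

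**Margin on the primary test.** The Wald z at 23/44 is (0.5227 − 0.37)/√(0.5227 × 0.4773/44) = 2.03. At 22/44 it is 1.72. This reproduces the plan's cutoff of 23. At the design rate of 61% (about 27 of 44), five responders would have to be lost to miss it. At the Phase 3 investigator-assessed rate of 73.2% (about 32 of 44), ten would.

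**The case against.** The case for leaving the rule alone has real substance, and most of it limits the scope.

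- **The primary link is not explicit.** CR/CRi is binary and has no censoring date. SAP 5.2.5 uses the any-therapy date only to end the on-treatment period, and 6.1.1.1 does not cite 5.3.3.4. Using the imputed date for the primary exclusion is the natural reading, but the SAP does not say so.
- **PFS and DoR move only for new induction therapy.** Therapy not recorded as induction does not censor them. A PD after the last dose moves the imputed date to PD + 1. A marrow shortly after the last dose can make a separate EOT marrow unnecessary.
- **A response is lost only if first documented after the last dose.** CR/CRi from earlier cycles stays.
- **Safety is partly covered.** Excluded events remain listed. VOD/SOS is reported to 2 years and has its own summary (if data permit), as do post-HSCT SAEs and deaths. Recording of nonserious events properly stops at the true start of new therapy.
- **The visit order is not guaranteed.** Footnote 19 says EOT should come first, so therapy may sometimes begin earlier.

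All of this stands. It reduces how often the rule does harm and how far that harm reaches. It does not explain why an imputed therapy date may precede an EOT visit that took place. The SAP already uses such a floor elsewhere: in 5.3.3.3 an incomplete death date may not fall before the day after last contact.

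**Conclusion.** The point holds for participants with an incomplete start date and no PD after the last dose. Its main consequence is for safety. With a completely missing date, the summarised post-dose window falls to 0 days, against 28 to 34 if therapy truly began on day 29 to 35. With a month-only date the window closes about 15 days early on average, if therapy began within 9 weeks. Treatment-emergent events are under-counted, which is the favourable direction.

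A reader might infer three stronger things that the documents do not support.

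- **That 63 days of safety follow-up are generally lost.** That needs a completely missing date and no true new therapy within 9 weeks.
- **That month-only dates usually remove response marrows.** Averaged over the marrow window, the share is 28% at most for true starts from day 29, and it drops quickly.
- **That the primary conclusion is in danger.** The link is unstated, any error would be conservative, and several responders would have to be lost at either plausible rate.

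The number of incomplete dates is unknown. Start and stop dates are collected prospectively, so it may be small. The percentages assume EOT at day 28 and calendar dates equally likely. It is also unclear whether relapse from CR/CRi, which SAP Appendix 1 defines separately from PD, counts as a PD date in the formula.

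**What to change.** In SAP 5.3.3.4, replace the term for last dose plus one day with max(last dose of study treatment, EOT visit date if performed) + 1. For month-only and year-only dates, use the later of the first day of the recorded period and that floor when it falls within the recorded period. Keep the cap at the therapy end date. If the floor falls after the recorded period, the existing last-day-of-period rule still applies.

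Do not use the last on-treatment disease assessment as a floor. SAP 3.5 defines on-treatment by the very date being imputed, so that would be circular.

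State in 6.1.1.1 that the 5.3.3.4 date is the one used for the primary exclusion, and say in 5.3.3.4 whether relapse from CR/CRi counts as PD.

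With EOT at day 28, no imputed month-only date then falls on or before EOT for any T in the table. The mean error drops from about 15 days to 0, 5.3 and 10.0 days at T = 29, 35 and 42. For a completely missing date with no PD, the summarised post-dose window rises from 0 to 28 days (25 to 31 across the visit window).

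The cost is SAP wording and a small derivation edit, with no new data. The downside is that, if a site began therapy before the EOT visit, the imputed start would be late and a post-therapy assessment could be credited to study drug. List every participant with an imputed start date and flag known cases of that kind.

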5.3.3.5. Other Dates

Imputation methods for other partial dates as follows:

- If the day of the month is missing for a start date used in a calculation, the first day of the month will be used to replace the missing date.
- If both the day and month are missing, the first day of the year is used.
- For stop dates, the last day of the month, or last day of the year is used if the day or day and month are missing, respectively.
- If the date is completely missing, no imputation will be performed.

6. ANALYSES AND SUMMARIES

6.1. Primary Endpoint(s)

6.1.1. CR/CRi

6.1.1.1. Main Analysis

The primary endpoint is the incidence of a participant with a best overall response of CR or CRi from date of the first dose to the end of treatment per investigator's assessment according to a modified Cheson Criteria.

Estimand strategy: The analysis applies while on treatment strategy ([Section 2.1.1](#)).

Analysis set: Safety analysis set ([Section 4](#)).

Intercurrent events and missing data: All data collected after an intercurrent event of subsequent anti-cancer therapy is excluded.

Analysis methodology: Test the null hypothesis $H_0: CR/CRi \text{ rate} \leq 37\%$ using the observed sample rate, actual sample size based on single binomial proportion test under normal approximation with empirical estimate of variance, ie, Wald test.

Estimate the CR/CRi rate per investigator's assessment and obtain the corresponding two-sided 95% CI using Wald method and Clopper–Pearson method separately for all participants in the safety analysis set from the time of first dose until the end of treatment. In addition, the frequency (number and percentage) of participants with CR, CRi, and CR/CRi will be tabulated.

Participants with death prior to first post-baseline assessment, new anti-cancer therapy started prior to first post-baseline assessment, and all post-baseline disease assessments missing will be considered as non-responders. Data collected after the end of treatment will be excluded from the analysis.

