### **Statistical Methods**

The statistical methods and analyses for the study will be described detail in the statistical analysis plan (SAP).

Specifically, the study will test the null hypothesis  $H_0$ : CR/CRi rate per investigator's assessment  $\leq 37\%$  vs the alternative hypothesis  $H_1$ : CR/CRi rate  $\geq 61\%$  where both hypotheses are consistent with those from study B1931022.

A sample size of 44 patients is planned to provide at least 90% power to reject the null hypothesis when the true CR/CRi rate  $\geq 61\%$  under the 1-sided significance level 0.025.

[figure not shown]
All other secondary endpoints will be descriptively summarized. Kaplan-Meier method will be used to summarize the time-to-event variables including duration of remission (DoR), progression-free survival (PFS) and overall survival (OS).

All safety analysis will be performed on the safety population. The number and percentage of patients with adverse events will be summarized by Medical Dictionary for Regulatory Activities (MedDRA) system organ class, preferred term, relationship to study drug, and severity.

Analyses of the PK data will be conducted on the PK concentration population. Descriptive summary statistics will be provided.

The anti-drug antibody (ADA) and NAb data are to be listed and summarized through frequency and percentage.

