### 9.2. Sample Size Determination

- A single-stage design will be used to test the null hypothesis ( $H_0$ ) with 1-sided 0.025 significance level that CR/CRi is  $\leq 37\%$ .
- A sample size of 44 patients is planned to provide at least 90% power to reject the null hypothesis ( $H_0$ : CR/CRi rate  $\leq 37\%$ ) when the true CR/CRi rate  $\geq 61\%$  under the 1-sided significance level 0.025, based on single binomial proportion test under normal approximation with empirical estimate for variance.
- Assuming exactly 44 patients are enrolled and treated, the null hypothesis will be rejected and it will be concluded that the study has demonstrated that the true CR/CRi rate exceeds 37% if 23 or more responders are observed. However, at the time of the analysis, the testing will depend on the actual number of patients enrolled.

A sufficient number of participants will be screened to achieve 44 participants enrolled and received at least one dose of inotuzumab ozogamicin.

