2.2. Study Design

This is an open-label, multi-center, single arm, phase 4 study of inotuzumab ozogamicin in Chinese adult participants with relapsed or refractory CD22-positive acute lymphoblastic leukemia (ALL), serving as a post approval commitment (PAC) study to confirm the efficacy, safety and pharmacokinetics (PK) of inotuzumab ozogamicin.

This study is designed to be a hypothesis test. A total of 44 participants will be enrolled to receive inotuzumab ozogamicin, which will provide at least 90% power to reject the null hypothesis ($H_0: CR/CRi \text{ rate} \leq 37\%$) when the true CR/CRi rate $\geq 61\%$ under the 1-sided significance level 0.025. Assuming exactly 44 participants are enrolled, the null hypothesis will be rejected and it will be concluded that the study has demonstrated that the true CR/CRi rate exceeds 37% if 23 or more responders are observed. However, at the time of the analysis, the testing will depend on the actual number of participants enrolled.

Two cycles of treatment of inotuzumab ozogamicin are recommended for hematopoietic stem cell transplant (HSCT) if the participant achieves response within the time period and a suitable donor is available, otherwise one more cycle, ie, the third cycle, may be considered. For participants not proceeding to HSCT, the maximum length of treatment is 6 cycles.

All cases of veno occlusive disease (VOD, also known as sinusoidal obstruction syndrome, SOS) irrespective of causality or severity will be reported as serious adverse events (SAEs) for up to 2 years after the first dose of inotuzumab ozogamicin. An independent hepatic event adjudication committee will evaluate safety for potential VOD/SOS events. Survival will be followed up to 2 years from the first dose of inotuzumab ozogamicin.

The end of the study is defined as the date of completion of survival follow-up for the last participant, which corresponds to up to 2 years from the date of last participant first dose.

This study will also use a hepatic events adjudication board (HEAB). The HEAB will review safety data, eg, potential cases of VOD.

No formal interim analysis will be conducted for this study.

This study will not use a data monitoring committee (DMC).

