5. GENERAL METHODOLOGY AND CONVENTIONS

5.1. Hypotheses and Decision Rules

5.1.1. Hypotheses and Sample Size

The primary objective of this study is to evaluate the treatment effect with inotuzumab ozogamicin, by demonstrating a greater CR/CRI rate than that observed with historical control. The statistical hypotheses for the primary endpoint CR/CRI per investigator's assessment are the same as those used in global pivotal Phase 3 Study B1931022, where based on review of the literature published historical data, the expected CR/CRI rate with historical control in the combined first and second salvage setting was approximately 37%. The observed results in the control arm in Study B1931022 didn't exceed 37% either. The study will test the null hypothesis H_0 : CR/CRI rate per investigator's assessment $\leq 37\%$ vs the alternative hypothesis H_a : CR/CRI rate $> 37\%$.

A single-stage design will be used to test the null hypothesis (H_0) with 1-sided 0.025 significance level. A sample size of 44 patients is planned to provide at least 90% power to reject the null hypothesis (H_0 : CR/CRI rate $\leq 37\%$) when the true CR/CRI rate $\geq 61\%$ under the 1-sided significance level 0.025, based on single binomial proportion test under normal approximation with empirical estimate for variance.

A sufficient number of participants will be screened to ensure 44 participants enrolled and received at least one dose of inotuzumab ozogamicin.

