5.1.2. Decision Rules

Assuming exactly 44 participants as planned in [Section 5.1.1](#) are enrolled and take at least one dose of treatment, the null hypothesis will be rejected and it will be concluded that the study has demonstrated that the true CR/CRI rate exceeds 37% if 23 or more responders are observed. However, at the time of the analysis, the testing will depend on the actual number of participants enrolled.

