5.2. General Methods

Except the hypothesis testing for CR/CRI, all analyses will be descriptive.

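### The 1-sided 0.025 level of the primary test is only nominal: the rule of 23 or more responders out of 44 has an exact type I error of 0.0277, which neither document states

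*SAP*

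**What the plan says.** Protocol 9.2 sets a single-stage test "with 1-sided 0.025 significance level that CR/CRi is" at most 37%. It plans 44 patients for at least 90% power at a true rate of 61%, under a normal approximation with the variance estimated from the data. SAP 5.1.1 repeats this ("based on single binomial proportion test under normal approximation with empirical estimate for variance"), and SAP 6.1.1.1 names the method for the analysis itself: "based on single binomial proportion test under normal approximation with empirical estimate of variance, ie, Wald test".

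SAP 5.1.2 turns this into a count. With exactly 44 treated, the study concludes that the true rate "exceeds 37% if 23 or more responders are observed". If the number differs, "the testing will depend on the actual number of participants enrolled". Apart from this test, SAP 5.2 says "all analyses will be descriptive".

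Two summary sections give the level without naming the approximation: the Statistical Methods part of the protocol synopsis ("under the 1-sided significance level 0.025") and SAP 2.2 ("under the 1-sided significance level 0.025. Assuming exactly 44 participants are enrolled, the null hypothesis will be rejected").

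For estimation, SAP 6.1.1.1 asks for both a Wald and a Clopper-Pearson two-sided 95% interval. Protocol 9.4.1 lists only the normal-approximation interval.

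**The concern.** This is the only hypothesis test in the study, so 0.025 is the only error rate the study quotes for a conclusion. Once the rule is a fixed count out of a fixed N, its type I error is a binomial tail probability that can be computed exactly. A Wald test at this sample size need not hold its nominal level, and here it does not. A reader of either document would take the chance of a false positive at 37% to be at most 0.025.

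A related gap would show at the boundary. If exactly 23 of 44 respond, the report would declare success while printing a Clopper-Pearson interval that contains 37%. Which interval belongs to the test is better stated before the data are seen than explained afterwards.

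**Working it through.** **Inputs.** Null rate p0 = 0.37, target rate p1 = 0.61, 1-sided level 0.025, power at least 90%, N = 44, rejection at 23 or more (Protocol 9.2; SAP 5.1.1 and 5.1.2). Wald test, with no continuity correction mentioned (SAP 6.1.1.1).

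**1. The plan's own figures reproduce.**

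- Sample size: n = [(1.960 + 1.2816)/(0.61 − 0.37)]² × 0.61 × 0.39 = 43.4, rounded up to 44.
- Approximate power at 44: Φ(0.24/√(0.61 × 0.39/44) − 1.960) = 0.904.
- Cut-off, from z = (x/44 − 0.37)/√(p̂(1 − p̂)/44) with p̂ = x/44:
  - x = 22: z = 0.1300/0.0754 = 1.725, p = 0.0423, not rejected.
  - x = 23: z = 0.1527/0.0753 = 2.028, p = 0.0213, rejected.

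So 44, at least 90% and 23 are all consistent with the stated method. With a continuity correction, 23/44 would give z = 1.877 and would not reject, so the published rule is the uncorrected one.

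**2. Exact properties of the rule at N = 44.**

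| Rule | P(reject) at 37% | P(reject) at 61% |
|---|---|---|
| 23 or more (planned) | 0.0277 | 0.9090 |
| 24 or more | 0.0133 | 0.8489 |

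The excess is 0.0277 − 0.025 = 0.0027, about 11% of 0.025. Because 37% is the edge of the null hypothesis, 0.0277 is the largest type I error of the rule under the null.

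**3. The level at other N.** The cut-off is re-derived from the actual N. The Wald rule then gives:

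| N | Cut-off | Exact level at 37% | Exact power at 61% |
|---|---|---|---|
| 40 | 21 | 0.0327 | 89.6% |
| 41 | 22 | 0.0218 | 86.9% |
| 42 | 22 | 0.0301 | 90.3% |
| 43 | 23 | 0.0201 | 87.8% |
| 44 | 23 | 0.0277 | 90.9% |
| 45 | 24 | 0.0186 | 88.6% |
| 46 | 24 | 0.0255 | 91.5% |
| 47 | 25 | 0.0172 | 89.3% |
| 48 | 25 | 0.0234 | 92.0% |
| 49 | 25 | 0.0313 | 94.2% |
| 50 | 26 | 0.0216 | 92.5% |

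The level exceeds 0.025 at N = 40, 42, 44, 46 and 49. One patient more or fewer than 44 brings it below 0.025, but exact power then falls below 90%.

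**4. The boundary result, 23/44 (52.3%).**

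- Wald 95% interval: 0.523 ± 1.960 × 0.0753 = 37.5% to 67.0%, which excludes 37%.
- Clopper-Pearson 95% interval: 36.7% to 67.5%, which includes 37%.
- Other methods at 23/44: score z = 2.098 (p = 0.0179) and mid-p = 0.0205, so both reject. The exact tail probability is 0.0277.

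**5. How often this matters.** At N = 44 the exact and Wald decisions differ only at exactly 23 responders. That result has probability 1.4% at a true rate of 37%, 6.0% at 61%, and 0.15% at 73.2%, the investigator-assessed rate for inotuzumab ozogamicin in all randomized patients of Study B1931022 (Protocol Table 4).

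**The case against.** The strongest reply is that nothing is hidden. Both documents name the normal approximation, the SAP calls it a Wald test, and the cut-off is published. A level declared under a named approximation is nominal by construction, and a statistician can obtain 0.0277 in one line. The threshold applied to the Wald p-value really is 0.025. Summary sections need not repeat the variance estimator. The Wald interval shares its name and variance with the test, and SAP 5.2 makes everything else descriptive, so what governs the decision is not in doubt. Enough patients are to be screened to reach 44 treated, so the spread over N = 40 to 50 is illustrative; SAP section 2 only allows that the number might deviate. The excess also applies only at the 37% boundary: at 30.9%, the investigator-assessed control rate in Study B1931022, the same rule rejects with probability 0.0025. Finally, editing the protocol means another amendment and ethics committee review for a change that alters no decision.

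Most of this stands, and it limits the point to a minor one. It does not remove it. Naming an approximation is not the same as stating the level it attains, and no section of either document does the latter. The documents put 0.025 on the rule, and the rule exceeds it. The cost argument bears on where and when the sentence is added. The interval labelling, taken alone, would be no more than a missing detail.

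**Conclusion.** The concern holds and is minor. With exactly 44 treated patients and the uncorrected Wald test, the planned rule has an exact type I error of 0.0277 against a stated 0.025. The power claim holds exactly (90.9%), and N and the cut-off follow correctly from the stated method. The calculation assumes independent responses with a common rate and takes 37% as the fixed null value. Score and mid-p methods agree with the planned decision at 23/44, and with 24 or more responders the exact test rejects as well. What needs correcting is the description of the error rate, together with the missing label on the two intervals.

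**What to change.** Keep N = 44, the cut-off of 23 and the Wald test.

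- **SAP 5.1.1 and 5.1.2, and Protocol 9.2**, add: The 1-sided 0.025 level is nominal. With 23 or more of 44, the exact binomial type I error at 37% is 0.0277 and the exact power at 61% is 90.9%. The exact level and power of the cut-off at the actual treated N will be reported.
- **SAP 6.1.1.1**, add: The Wald interval corresponds to the primary test; the Clopper-Pearson interval is descriptive.
- **Protocol 1.1 and SAP 2.2**: put the word nominal before the 0.025.

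The cost is two or three sentences plus one added word in each of the two summaries. There are no extra patients and no change to the endpoint, test or decision. The stated error rate becomes slightly less favourable. The protocol wording needs an amendment; the SAP wording can be changed first and the protocol aligned at its next amendment.

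An exact test is an alternative but is not required. At N = 44 it needs 24 or more responders, with level 0.0133 and power 84.9%. Keeping at least 90% power under it takes N = 48 (25 or more; level 0.0234, power 92.0%). Power dips to 89.98% at N = 49 and stays above 90% from N = 50 to 69, with a minimum of 90.6% at N = 51.
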